### Study Schema

#### Key Study Time Points as related to Hematopoietic Cell Transplant (HCT):

- **Enrollment** (signing of consent, confirmation of eligibility - occurs during the pre-HCT work-up)
- **Study Entry** (DXA scan, blood and urine tests begin during pre-HCT work-up until admission or at the time of admission, daily Vitamin D/Calcium begins upon admission to the hospital)
- **Randomization** (Pamidronate versus no Pamidronate) occurs at the Day 90 post-HCT milestone visit
- **Final Study Visit** occurs at the Day 360 post-HCT milestone visit

#### Treatment Plan:

##### All subjects:

**Vitamin D and Calcium Supplementation** per Section 7.3 begin prior to HCT preparative regimen start (e.g. on day of admission for transplant) and continue daily through day 360 post-HCT milestone visit

##### Pamidronate Group

**Pamidronate (P)** 1 mg/kg IV (to max dose of 60 mg) over 4 hours on Day 90, Day 180, and Day 270 post-HCT

## List of Abbreviations

AE	Adverse Event
AI	Adequate Intake
ALL	Acute Lymphoblastic Leukemia
AML	Acute Myeloid Leukemia
BMC	Bone Mineral Content
BMD	Bone Mineral Density
BMI	Body Mass Index
BP	Bisphosphonate
CFR	Code of Federal Regulations
CML	Chronic Myelogenous Leukemia
CNS	Central Nervous System
CPRC	Cancer Protocol Review Committee
CRF	Case Report Form
CTCAE	Common Terminology Criteria for Adverse Events
CTSI	Clinical and Translational Science Institute
CTX	Carboxy Terminal Collagen Crosslinks
DPD	Deoxypyridinoline
DSMC	Data and Safety Monitoring Council
DSMP	Data and Safety Monitoring Plan
DXA	Dual-energy X-ray Absorptiometry
eCRF	electronic case report form
EDTA	Ethylenediaminetetraacetic Acid
FDA	Food and Drug Administration
FFQ	Food Frequency Questionnaire
FHCRC	Fred Hutchinson Cancer Research Center
GCP	Good Clinical Practice
GnRH	Gonadotropin-releasing Hormone
GVHD	Graft-Versus-Host Disease
HCT	Hematopoietic Cell Transplantation
HIPAA	Health Insurance Portability and Accountability Act of 1996
ICH	International Conference on Harmonisation
IDS	Investigational Drug Services
IL	Interleukin
IND	Investigational New Drug
iPTH	Intact Parathyroid Hormone
IRB	Institutional Review Board
IV	Intravenous
LBMC	Lumbar Bone Mineral Content
LBMD	Lumbar Bone Mineral Density
NCI	National Cancer Institute
OCN	Osteocalcin
OCP	Oral Contraceptive Pill
OH	Hydroxy
OI	Osteogenesis Imperfecta
OnCore	University of Minnesota's data capture system
OPG	Osteoprogerin
OTC	Over-the-counter
P1NP	Procollagen Type 1 Terminal Peptide
PHI	Protected Health Information

PI	Principal Investigator
PN	Parenteral Nutrition
pQCT	Peripheral Quantitative Computed Tomography
qs	Sufficient Quantity
RANKL	Receptor Activator of Nuclear Factor- $\kappa$ B Ligand
RDA	Recommended Dietary Allowance
REPA	Report of External Professional Activities
Rx	Prescription
SAA	Severe Aplastic Anemia
SAE	Serious Adverse Event
SD	Standard Deviation
SST	Serum Separation Tube
TBD	To Be Determined
TBMD	Total Body Bone Mineral Density
TNF- $\alpha$	Tumor Necrosis Factor Alpha
UMN	University of Minnesota
USP	United States Pharmacopeia

## **1 Introduction, Background and Rationale**

Low bone mineral density (BMD) is common in children treated with hematopoietic cell transplantation (HCT) in both early and late follow-up (1-7). Low BMD in childhood is expected to increase the risk of early osteoporosis and increase the risk of fracture due to low peak bone mass (7-11). This has serious individual and societal implications due to impaired mobility and ability to participate in activities of daily living that occurs after fracture. In older adults, fracture has even been associated with an increased risk of death.

Bone health is dependent on a balance between bone resorption and bone formation; when this balance is disrupted bone loss and ultimately osteoporosis develop. BMD decreases in the first 6 months after HCT (1). A recent study has shown that bone resorption is significantly increased by 100 days after pediatric HCT and remains elevated through at least 180 days after HCT (12), which offers an opportunity for intervention.

### **1.1 Pamidronate Disodium**

Pamidronate is a bisphosphonate (BP) that inhibits bone resorption and thus can increase bone density by shifting the balance towards bone formation. Although its mechanism of antiresorptive action is not completely understood, several factors are thought to contribute to this action. Pamidronate disodium adsorbs to calcium phosphate (hydroxyapatite) crystals in bone and may directly block dissolution of this mineral component of bone. In vitro studies also suggest that inhibition of osteoclast activity contributes to inhibition of bone resorption. In animal studies, at doses recommended for the treatment of hypercalcemia, pamidronate disodium inhibits bone resorption apparently without inhibiting bone formation and mineralization (13).

The Food and Drug Administration (FDA) has approved pamidronate for use in osteolytic bone metastasis associated with metastatic breast cancer or multiple myeloma, hypercalcemia of malignancy (with adequate hydration), and Paget's disease in adults. It is also frequently used to treat post-menopausal osteoporosis and has been shown to be effective in preventing post-transplant bone loss in adults (14-16).

### **1.2 Pamidronate in Children**

Pamidronate has not been approved for use in children but clinical trials have been conducted in children with various disorders causing osteoporosis or low bone density. In children, pamidronate and other BPs have been used safely and effectively to treat the most debilitating form of childhood osteoporosis, osteogenesis imperfecta (OI) (17, 18). The first case report of beneficial effects

of BP treatment in OI was published in 1987 (19) and was followed by over 30 clinical trials (20-22). In these studies, the most commonly used BP was intravenous pamidronate at a dose of 0.6 to 3.75 mg/kg/day over 1 to 3 days every 1 to 6 months (23, 24). The patients' age was 0.04 to 18 years and follow-up lasted up to 9 years. The reported therapeutic effects included improvement in bone density (increase in lumbar spine BMD Z-score of about 2.6 or in spine BMD of 42 to 48%), grip strength, vertebral height, cortical thickness, trabecular number, decreased bone turnover, increased mobility, and decreased fracture rate. Due to these beneficial effects, pamidronate has become the standard of care in treating severe OI (25). BPs are increasingly prescribed in children with other diseases, for example neuromuscular disorders (26-28) or idiopathic juvenile osteoporosis (29, 30) with improvements noted in the spine, femoral neck, and/or total body BMD Z-scores and a reduced fracture rate. Pamidronate has also been used in pediatric burn patients to prevent bone loss (31).

There has been 1 retrospective observational study that found BP therapy improved BMD in pediatric HCT recipients (32). The study included children who survived at least 1 year after allogeneic HCT with 48 control patients receiving calcium and vitamin D and 18 patients also receiving BP therapy (17 of the 18 patients received pamidronate for the majority of the study as monthly infusions of 1 mg/kg for 6 months to 2 years). Baseline and follow- up dual energy x-ray absorptiometry (DXA) scans (mostly at the lumbar spine) were compared. The annualized increase in BMD was 10% per year for the control patients and 33% per year for patients that also received BP. To account for expected age-related increase in BMD, the interval change in BMD Z-scores was calculated. The annualized median change in BMD Z-scores per year was +0.12 among the control patients and +1.43 for the BP group. Thus, in this non-randomized retrospective study, BP-treated HCT recipients had a significantly greater increase in BMD than control patients.

Short- and long-term safety of BPs for children with compromised bone health has been recently assessed on behalf of the Drugs and Therapeutics Committee of the Pediatric Endocrine Society (25). In most studies, no serious side effects have been reported with the exception of 1 case of iatrogenic osteopetrosis in a 12 year-old boy treated with higher than recommended doses of pamidronate (2.2 to 3.4 mg/kg every 3 weeks and then less frequent intervals between 7/4 and 10^1/2 years of age) for idiopathic bone pain with a marked elevation of alkaline phosphatase (33). More likely side effects are transient hypocalcemia (24, 34), which can be prevented/mitigated by calcium and vitamin D supplementation, and an acute-phase reaction, including influenza-like symptoms (24, 35-38), which can be mitigated by anti-pyretic/anti-inflammatory agents. Nephrotoxicity has

been reported in adults treated with pamidronate (39, 40), but no adverse effect on renal function has been reported in children treated with pamidronate or other BPs. There has been some concern about long-term effects due to deposition of BPs in the skeleton. A half-life of more than 10 years has been reported in adults (41). Long-term release of BPs has been shown in children who were treated with pamidronate for 4 to 10 years (42). Fractures have been described in OI patients following pamidronate discontinuation, at the interface between the high density (pamidronate-treated) and low density (newly formed, pamidronate-naïve) bone (43-45). It is thought, however, that this risk may be limited to patients who have persistent risk factors such as a genetic defect (e.g., collagenopathy) as opposed to transient exposures. It is unlikely that these potential long-term consequences are pertinent to this study, which requires short-term exposure to pamidronate and excludes children with any underlying genetic abnormality in bone remodeling.

## **2 Pamidronate Disodium (Investigational Agent)**

### **2.1 Description**

Molecular formula:  $C_3H_9NO_7P_2Na_2 \cdot 5H_2O$

Molecular weight: 369.1

30 mg single use vial: 3 mg/mL pamidronate disodium, 47 mg/mL mannitol, United States Pharmacopeia (USP); water for injection, USP, sufficient quantity (qs); and phosphoric acid to adjust pH.

90 mg single use vial: 9 mg/mL pamidronate disodium, 37.5 mg/mL mannitol, USP; water for injection, USP, qs; and phosphoric acid to adjust pH.

### **2.2 Indications**

Pamidronate disodium was approved by the FDA in 1991 for the treatment of osteolytic bone metastasis associated with metastatic breast cancer or multiple myeloma, hypercalcemia of malignancy (with adequate hydration), and Paget's disease in adults.

Pamidronate has not been FDA-approved for pediatric use but given previous data in children (refer to Section 1.2), standard safety monitoring following HCT, and the additional safety evaluations included in this protocol, the risk to subject safety is relatively low.

### **2.3 Study Drug Availability**

For the purposes of the study vials of pamidronate disodium will be purchased by

the study through each institution's Investigational Drug Service (IDS).

Study drug inventory will be documented.

#### **2.4 Packaging, Storage, and Preparation**

##### **Packaging and Labelling**

The immediate package of an investigational drug intended for human use shall bear a label with the statement:

**Caution: New Drug--Limited by Federal law to investigational use.**

##### **Storage**

Vials of pamidronate disodium solution must be stored at 20 to 25°C.

##### **Preparation for Infusion**

Pamidronate disodium solution will be diluted to the recommended subject dose in sterile sodium chloride 0.45% or 0.9% or dextrose 5%. The drug will be completely dissolved before the solution is withdrawn. Parenteral drug products will be visually inspected for particulate matter and discoloration prior to administration, whenever solution and container permit. Refer to the package insert for complete details

#### **2.5 Final Reconciliation and Destruction of Study Drug**

At the completion of the study, there will be a final reconciliation of study agents that were purchased, consumed, and remaining at the study site. This reconciliation will be logged on the drug reconciliation form, signed and dated. Any discrepancies noted will be investigated, resolved, and documented prior to destruction of unused study drug.

Any leftover drug will be destroyed on site according to institutional policies.

### **3 Study Objectives and Hypotheses**

#### **3.1 Primary Hypothesis**

The primary hypothesis is subjects treated with pamidronate and calcium and vitamin D (Pamidronate Group) will have higher lumbar bone mineral content (LBMC adjusted for height, age, sex, Tanner stage and race) measured by DXA 1 year post-HCT than subjects receiving calcium and vitamin D alone (Control Group).

#### **3.2 Secondary Hypotheses**

The secondary hypotheses are:

- Subjects treated with pamidronate will have higher total body BMC (TBMC; excluding head; adjusted for height, age, sex, Tanner stage, and race) measured by DXA 1 year post-HCT compared to the Control Group.
- Subjects treated with pamidronate will have higher total BMD, cortical BMD, trabecular BMD, and estimated bone strength measured by peripheral quantitative computed tomography (pQCT) 1 year post-HCT compared to the Control Group.
- Cytokine levels will increase rapidly in the first 3 weeks after HCT, preceding an increase in markers of bone resorption.
- In the Control Group, increased cytokine levels and receptor activator of nuclear factor- $\kappa$  B ligand (RANKL)/osteoprogenin (OPG) ratio 3 weeks post-HCT will be associated with decreased BMC and BMD 1 year after HCT.
- Markers of bone resorption will increase in the first 3 months after HCT, will remain elevated until at least Day 180 in the Control Group, but will decrease after initiation of pamidronate at Day 90 in the Pamidronate Group.
- Markers of bone formation, including osteocalcin (OCN), will decrease in the first 3 months after HCT and in the Control Group lower OCN levels at Day 90 will be associated with lower BMC and BMD 1 year post-HCT.

## 4 Study Design

This is a Phase 2, open-label, randomized, controlled clinical study of pediatric subjects (defined as  $\geq 1$  year, but  $\leq 20$  years of age) treated with pamidronate with calcium and vitamin D versus calcium and vitamin D alone following HCT.

All subjects will receive a supplemental dose of vitamin D (based on vitamin D (D2+D3) level) beginning upon admission to the hospital for the HCT and calcium if they are not meeting the recommended dietary allowance (RDA) or if their serum calcium is low (based on ionized calcium level). Refer to Section 7.3 for supplementation guidelines.

At the Day 90 post-transplant visit, subjects will be randomized to receive one of the following treatment plans through the Day 360 post-transplant visit:

- Control Group: continue determined vitamin D per day and calcium supplementation, as appropriate to meet the RDA requirement. Refer to Section 7.1 for supplementation guidelines.
- Pamidronate Group: continue determined vitamin D per day and calcium supplementation, as appropriate to meet RDA requirement, AND 3 single IV infusions of 1 mg/kg (to a max of 60 kg) pamidronate at 3-month intervals (Day 90, 180 and 270) post-transplant. Refer to Section 7.3 for supplementation guidelines

Laboratory evaluations, DXA, and pQCT will be performed at specified time points per section 8 to monitor safety and evaluate treatment efficacy.

## **5      Subject Selection**

This study will evaluate bone loss in pediatric patients undergoing a hematopoietic cell transplant (HCT). Study entry is open to persons  $\geq 1$ , but  $\leq 20$  years of age regardless of gender, race or ethnic background. While there will be every effort to seek out and include females and minority patients, the patient population is expected to be no different than that of hematopoietic cell transplant studies for hematologic malignancies and severe aplastic anemia at the University of Minnesota and Fred Hutchinson Cancer Research Center.

Patients will be consented and screened during their pre-transplant evaluation. Vitamin D and calcium, if indicated, will be started at the time of admission for transplant.

### **5.1    Inclusion Criteria**

All of the following criteria must be met:

#### **5.1.1   Patients in one of the below disease categories:**

**5.1.1.1** Allogeneic hematopoietic cell transplant for hematologic malignancy (i.e. leukemia, lymphoma including ALL, AML, CML, NHL, HL) in complete remission; myelodysplastic syndrome (active dysplasia and/or blasts are permitted, but must not have active leukemia) who will be receiving a myeloablative preparative regimen, **OR**

**5.1.1.2** Non-malignant diseases including idiopathic severe aplastic anemia (SAA) and other bone marrow failure disorders, hemoglobinopathies, adrenoleukodystrophy, immune deficiencies/dysregulation disorders who will be receiving myeloablative or reduced toxicity preparative regimens that meet the following criteria:

**5.1.1.2.1** Regimens include those that are TBI based if the TBI dose is  $> 500$ cGy single dose or  $> 800$ cGy fractionated, or doses  $< 500$  cGy if combined with busulfan or treosulfan. These also include chemotherapy only based regimens that contain myeloablative doses of busulfan ( $>8$ mg/kg) or treosulfan without TBI

**5.1.1.2.2** Patients with severe aplastic anemia are eligible regardless of conditioning regimen

**5.1.2** Male or female  $\geq 1$  but  $\leq 20$  years of age at time of study enrollment

**5.1.3** Patient or parent(s)/legal guardian(s) is able and willing to provide informed consent. Assent will be obtained per local institutional policy. Subjects who turn 18 during the course of the study will be consented at that time of their next visit by a member of the research staff.

## **5.2 Exclusion Criteria**

Patients will be excluded from participation in the study if any of the following conditions exist:

- 5.2.1** History of a primary bone malignancy involving the lumbar spine
- 5.2.2** Treatment with other biphosphonates, Denosumab, or Teriparatide within one year prior to enrollment
- 5.2.3** Pregnancy or breastfeeding – menstruating females must have a negative pregnancy test prior to study enrollment and agree to repeat pregnancy testing and contraception use per protocol as pamidronate is Pregnancy Category D – positive evidence of human fetal risk based on adverse reaction data
- 5.2.4** Renal insufficiency, defined as creatinine level greater than the upper limit of normal for age
- 5.2.5** Hereditary metabolic bone disease or skeletal dysplasia (e.g., osteopetrosis or OI) or primary hyperparathyroidism
- 5.2.6** Non-malignant diseases with underlying metabolic defects that may affect bones such as Hurler's syndrome and other Mucopolysaccharidoses and osteopetrosis, or diseases where the use of hematopoietic cell transplant itself is still under investigation, primarily, epidermolysis bullosa.
- 5.2.7** Patients with diseases that have increased sensitivity to chemotherapy or radiation including (but not limited to) Fanconi anemia, dyskeratosis congenita.
- 5.2.8** Clinically significant fractures as defined by ISCD (a long bone fracture of the lower extremities, vertebral compression fracture, or two or more long bone fractures of the upper extremities) (88,89) indicated by a cast or a spine x-ray within the last 2 weeks
- 5.2.9** Known or suspected allergy to pamidronate or related products
- 5.2.10** Planned administration of an investigational study drug or agent that either can interact with pamidronate or have an independent effect on bone mineral density within the 4 weeks prior to randomization (Day 90) or planned use during study participation (Day 90 through Day 360)
- 5.2.11** Impending invasive dental procedure that would be expected to occur during study participation (through Day 360)

## **6 Study Registration and Randomization**

Registration will occur after the patient or parent/guardian has signed the appropriate subject consent and eligibility is confirmed, but before any treatment has been administered. To be eligible for registration to this study, the patient must meet each criteria listed on the eligibility checklist case report form based on the eligibility assessment documented in the patient's medical record.

### **6.1 Registration with the Masonic Cancer Center Clinical Trials Office**

Upon completion of the screening evaluation, eligibility confirmation and obtaining written consent, the study coordinator or designee will enroll the patient into OnCore.

OnCore will automatically generate an email alerting key study personnel of the registration.

### **6.2 Randomization (Day 90 Post-HCT Visit +/- 14 days)**

Randomization to pamidronate (Pamidronate Group) or no pamidronate (Control Group) will occur at Day 90 (+/- 14 days) by the institutional study coordinator based on the randomization schedule developed by the study statistician and entered into OnCore.

A brief review of continuing eligibility will be done and subjects will not be eligible for randomization if one or more of the following are true:

- Vitamin D ( $D_2+D_3$ )  $<20$  ng/ml as use of pamidronate is contraindicated due to potentially higher risk of hypocalcemia. Levels should be measured within 14 days prior to randomization.\*\*†
- serum creatinine is  $> 2$  times the baseline value (at Study Entry) - perform within 14 days prior to randomization
- an investigational study drug or agent, including biphosphonates, Denosumab, or Teriparatide, was administered within the previous 4 weeks or is planned for use during study participation (Day 90 through Day 360)
- positive pregnancy test (performed within 14 days prior to randomization)
- Inability to successfully complete a DEXA scan
- the parent or adult patient refuse randomization
- disease relapse has occurred

The randomization will be stratified by age with 2 strata:  $< 10$  years old and  $\geq 10$  years old.

If the patient is ineligible for or refuses randomization, no further research related procedures or treatment will occur after the Day 90 visit; however permission to continue review of the patient's medical record through the Day 360 visit for routine clinical information is embedded within the consent form document. This information will be collected only if the patient continues care at the enrolling

institution. Patient care will be at the discretion of the treating physician(s) and independent of this study.

OnCore will automatically generate an email alerting key study personnel of the randomization (or lack of).

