## 7 Treatment Plan

### 7.1 Vitamin D and Calcium Supplementation

All subjects will receive a supplemental vitamin D (based on Vitamin D2+D3 levels beginning upon admission to the hospital for the HCT (54, 55). Vitamin D and Calcium supplementation will be determined by a combination of Vitamin D levels, ionized calcium levels, calcium intake, PTH, and TPN. See section 7.3 for supplementation guideline charts. In subjects who require parenteral nutrition (PN) and have normal vitamin D (D2+D3) level, vitamin D will be given as part of multivitamin supplementation.

- Adult multivitamin preparations contain 200 IU of cholecalciferol per 10 ml (or 5 mcg of ergocalciferol, equivalent to 200 IU of ergocalciferol, per 10 ml).

Pediatric multivitamin preparations contain 400 IU of cholecalciferol per 5 ml. (of 10 mcg of ergocalciferol, equivalent to 400 IU of ergocalciferol, per 5 ml)

If a subject's serum vitamin D (D2+ D3) is <30 ng/mL at any of the designated time points starting from study entry through Day 360 post-HCT (including 8 week rechecks for subtherapeutic levels), additional supplementation with vitamin D will be administered to maintain a serum level between 30 and 70 ng/mL according to the protocol as outlined in Section 7.

If serum vitamin D (D2+ D3) levels are low and supplementation is begun, levels will be re-checked after 8 weeks at the next scheduled study visit. Although the proposed regimen should normalize vitamin D level within 6-8 weeks (57), if the target range is not reached, supplementation will be continued for additional 8 weeks, and serum vitamin D level (D2+D3) repeated at the end of treatment. Subjects with vitamin D level (D2+D3) <20 ng/ml at Study Entry will be excluded from analyses of bone turnover markers until vitamin D level (D2+D3) normalizes but otherwise will be included in all analyses.

\*\* Measurement of Vit (D2+D3) levels is recommended instead of 25-hydroxy-Vitamin D level, as they reflect vitamin D stores accurately and independently of whether the subject is on VitD2 (ergocalciferol) or VitD3 (cholecalciferol) supplementation. As 25-hydroxyVitamin D assay mainly measures VitD3 stores, it can underestimate overall vitamin D stores in patients supplemented with

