**7.4 Pamidronate**

**7.4.1 Treatment Plan**

Subjects randomized to the Pamidronate Group will receive 3 single doses of pamidronate at 3-month intervals (Day 90 +/-14 days, Day 180 +/-14 days, and Day 270 +/-30 days).

Note: All time point specific laboratory testing procedures (sections 8.1 and 8.3) must be collected prior to the pamidronate infusion (except those specifically designated post infusion); however for ease of scheduling the consultations as well as the Day 90 DXA and Day 90 pQCT may be performed after the infusion as long as done within the +/-14 day window. Ionized calcium or corrected calcium, and Vitamin D levels (D2+D3) will be drawn prior to pamidronate infusions. If either are low, the subject should receive supplemental calcium and/or Vitamin D per Section 7.3. If the subject is receiving supplemental calcium, an ionized or corrected calcium level should be drawn after the pamidronate infusion end but prior to discharge from clinic on the day of the pamidronate.

Prior to each infusion the patient will be assessed and pamidronate will be held if:

- Serum creatinine is > 2 times the baseline (Study Entry) level – refer to section 7.3.2 for monitoring plan – the pre-treatment creatinine may be done anytime within 72 hours prior to the planned pamidronate administration

- Pregnancy test is positive (subject will permanently discontinue study drug) per section 7.3.5 – pregnancy testing may be done anytime within 72 hours prior to the planned pamidronate administration

Pamidronate 1 mg/kg (to a max dose of 60 mg) will be administered via a single IV infusion over 4 hours using a line separate from all other drugs. Dosing will be based on the patient's actual weight or, if overweight, on ideal body weight (IBW). This will be followed by a normal saline flush of 20 cc total given at the same rate as the pamidronate.

Premedication: Subjects will be given 15 mg/kg acetaminophen (or maximum of 500 mg) prior to pamidronate infusion then every 4 hours as needed for a maximum of 24 hours.

Post-Pamidronate Infusion Laboratory Tests: A serum calcium level will be done after the pamidronate infusion end but prior to discharge from clinic on the day of the pamidronate.

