#### **7.4.6 Criteria for Discontinuation**

Subjects receiving pamidronate will discontinue pamidronate if any of the following conditions exist:

- Clinically significant allergic reaction (tongue or facial swelling or wheezing) to pamidronate
- Subsequently meets any of the study exclusion criteria (section 5.2) except for clinically significant current fracture, in which case pamidronate will be continued
- If creatinine level increases to > 2 times baseline level and a dose of pamidronate must be skipped for a 2nd time per section 7.3.2.
- Unacceptable toxicity (e.g. osteonecrosis of the jaw)
- Positive pregnancy test - Refer to section 9.3 regarding the reporting of pregnancy during study treatment.
- Disease relapse
- Subject's well-being, in the opinion of the Investigator, would be compromised by continuation of pamidronate administration.

These subjects will continue to be enrolled in the study, receiving vitamin D/calcium and participating in study procedures as planned unless contraindicated. An exception to this plan is for those patients who have a worsening of their disease (relapse) and discontinue routine post-HCT follow-up at the enrolling institution. In this situation, patients would be taken off study with no further study procedures.

Subjects who discontinue pamidronate treatment after the first dose (Day 90) will be included in the statistical analyses as members of the Pamidronate Group under the principle of intention-to-treat.

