c Including Tanner staging of pubertal development.

d Females >10 years only.

e If documentation of a negative pregnancy test within 7 days prior to DXA scan is available, the pregnancy test does not need to be repeated.

f If result is below the lower limit of normal refer to section 7.2 and 7.3.

g Subjects who have vitamin D levels ( $D_2+D_3$ ) <20 ng/ml at Day 90 will not be eligible for randomization per section 6.2.

h L1-L4 and total body scans with body composition.

i Subjects at the University of Minnesota (UMN) only.

j All subjects will begin taking supplemental vitamin D per day and calcium, if needed, to meet recommended dietary allowance (RDA) requirement upon admission to the hospital for the HCT and continue through Day 360. If a subject has low vitamin D ( $D_2+D_3$ ), dietary calcium intake is below RDA, or the ionized/or corrected calcium level is below the normal range, additional vitamin D and/or calcium supplementation will be given per Section 7.3.

k For subjects randomized to the Pamidronate Group, 1 mg/kg (60 mg max) will be administered via intravenous (IV) infusion over 4 hours. Subjects will be given 15 mg/kg acetaminophen (or maximum of 500 mg) prior to infusion then every 4 hours as needed for a maximum of 24 hours. Postmenarchal subjects randomized to pamidronate will be put on an oral contraceptive pill (Loestrin or Orthocept or other OCP that contains 30 mcg ethinyl estradiol), birth control patch or other effective method of birth control. The results of the serum creatinine and pregnancy test (if applicable) must be reviewed before drug administration.

l Pamidronate patients only

m Serum creatinine level and spot urine collected the morning after each pamidronate infusion; however if not feasible at that time may be done anytime within 7 days after pamidronate infusion. A morning collection is preferred, but not mandatory. The time of the urine collection must be recorded.

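### Vitamin D below 20 ng/mL bars randomisation as a contraindication to pamidronate, but does not hold doses 2 and 3

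*Combined protocol and SAP*

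**What the plan says.** Section 6.2 makes a child ineligible for randomisation if vitamin D is below 20 ng/mL, measured within the previous 14 days, on the ground that "use of pamidronate is contraindicated due to potentially higher risk of hypocalcemia". Footnote g of the schedule in section 8.1 repeats the rule for that visit: children below the limit "ng/ml at Day 90 will not be eligible for randomization per section 6.2".

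Pamidronate is then given three times: "Day 90 +/-14 days, Day 180 +/-14 days, and Day 270 +/-30 days". The dosing rules in section 7.4.1 have two parts.

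- Ionized or corrected calcium and vitamin D "will be drawn prior to pamidronate infusions. If either are low, the subject should receive supplemental calcium and/or Vitamin D per Section 7.3".
- "Prior to each infusion the patient will be assessed and pamidronate will be held if" one of two conditions is met: creatinine more than twice baseline, or a positive pregnancy test.

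Footnote k of section 8.1 matches the second part: "The results of the serum creatinine and pregnancy test (if applicable) must be reviewed before drug administration". Vitamin D is not among the results to be reviewed.

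Section 7.4.6 lists reasons to stop pamidronate. None is a vitamin D level. The nearest is a general clause: "Subject's well-being, in the opinion of the Investigator, would be compromised by continuation of pamidronate administration".

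**The concern.** The reason given in section 6.2 is pharmacological. If the drug is contraindicated below 20 ng/mL because of hypocalcemia risk, that applies to every infusion. The limit is nevertheless written as an entry criterion and does not reappear in the rules for later doses. A site that follows the dosing text would be entitled to infuse a child at Day 180 or Day 270 under a condition the same protocol calls a contraindication. Section 7.4.3 describes hypocalcemia as a common side effect of pamidronate in children.

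What is at stake is the safety of individual children and consistency between the two sites, since two investigators could act differently on the same result.

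**Working it through.** No statistical calculation applies to the main point. It rests on a comparison of texts, followed by a little date arithmetic on what a hold would involve.

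**1. Which randomisation bars carry over to later doses?**

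| Bar in section 6.2 | Rule for doses 2 and 3 |
|---|---|
| Creatinine more than twice baseline | Hold in 7.4.1; skip rule in 7.4.2 |
| Positive pregnancy test | Hold in 7.4.1; stop in 7.4.6 |
| Prohibited or investigational agent | 7.6, and 5.2 through 7.4.6 |
| Relapse | Stop in 7.4.6 |
| Vitamin D below 20 ng/mL | None |

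The other two bars, refusal and inability to complete a DXA scan, do not concern drug safety.

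**2. Is the vitamin D limit anywhere else?** Section 7.4.6 stops the drug if a child later meets a section 5.2 exclusion, but 5.2 has no vitamin D criterion. The charts in 7.3.3 (10-19 ng/mL) and 7.3.4 (below 10 ng/mL) give supplement doses and recheck times and do not mention pamidronate. By dose: Day 90 has a limit, Day 180 has none, Day 270 has none. That is 2 of 3 doses without one.

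**3. Does supplementation stand in for a hold?** Section 7.4.1 requires the sample before the infusion but sets no draw window for it and does not require the result before dosing. The Revision History (revision 6) shows that the 14-day window in 6.2 was chosen to allow for laboratory turnaround, so a sample taken at the infusion visit may not be reported in time. Section 7.1 expects supplementation to normalise vitamin D in 6-8 weeks, that is 42-56 days. Supplementation begun on the day of the infusion cannot be relied on to correct the level before that infusion.

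**4. What protection remains?** There is calcium before the infusion with supplementation if low, a same-day calcium after it, a telephone assessment at 1 week, the stop after a grade 4 toxicity (7.4.4), and the judgement clause. None of these is a vitamin D threshold. Protection is thinnest for a child not on TPN with vitamin D 10-19 ng/mL and normal calcium. Those charts in 7.3.3 contain no weekly calcium check and drop the 50 mg/kg calcium when PTH is below 65.

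**5. Could a recheck fit the visit windows?**

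- Dose 2: 180 - 14 = Day 166 to 180 + 14 = Day 194, a span of 28 days.
- Dose 3: 270 - 30 = Day 240 to 270 + 30 = Day 300, a span of 60 days.
- The charts for levels below 20 ng/mL recheck at 8 weeks (56 days). For that recheck to fall inside the window, the low sample must be taken by 194 - 56 = Day 138 for dose 2, or by 300 - 56 = Day 244 for dose 3.

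Day 138 is 166 - 138 = 28 days before the dose 2 window opens. Day 244 is only 4 days after the dose 3 window opens. A recheck meant to decide a dose will therefore usually have to come earlier than the chart's 8 weeks. The documents give no time to reach 20 ng/mL, so the share of held doses that could still be given in the window is unknown.

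**The case against.** The best defence is that the plan states an action and may intend it. Section 7.4.1 has calcium and vitamin D drawn before infusions and says to supplement if either is low; the hold list follows and omits both. Low calcium, the direct measure of the feared harm, is not a hold either. That pattern fits a deliberate approach of a strict limit at entry, then supplementation and monitoring. Section 6.2 itself speaks only of a potentially higher risk.

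This stands in part. The documents do not say whether the omission is deliberate, and the gap is a missing hold, not missing monitoring. But the defence does not remove the conflict: no text limits the contraindication to the first dose.

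The second objection is rarity. Every randomised child is at or above 20 ng/mL within 14 days before randomisation and is supplemented toward 30-70 ng/mL (7.1), so a case needs a fall despite treatment. This stands, and it limits how much weight the point can carry.

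The third concerns iPTH. The 8.1 table marks iPTH only at Study Entry, Day 90 and Day 360. A reader might infer that the value deciding therapeutic calcium would be unavailable at Days 180 and 270. The documents do not support that. Section 7.2 applies its rule on vitamin D of 10-20 ng/mL with raised iPTH at any time through Day 360, which implies that iPTH would be obtained when vitamin D is in that range. It is unscheduled, not excluded.

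**Conclusion.** The inconsistency is real. A limit justified as a contraindication to the drug is applied before dose 1 and absent for 2 of the 3 doses, leaving only unspecific investigator judgement. It should be fixed because the wording permits what section 6.2 rules out.

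The count of doses describes the gap in the rules and does not measure risk. A reader might infer that vitamin D-deficient children would often be infused, or that hypocalcemia would follow. The documents give no basis for either: they contain no vitamin D distribution at Days 180 or 270 and no hypocalcemia rate by vitamin D level, and the calcium checks offer partial protection. Nor can it be concluded that the omission was an oversight.

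The conclusion assumes only that the reason stated in 6.2 means what it says and that sites follow 7.4.1 and footnote k as written.

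**What to change.** Add vitamin D below 20 ng/mL to the hold list in 7.4.1, and add the vitamin D result to footnote k, drawn within 14 days before the infusion as in 6.2. If the level is low, supplement per 7.3, recheck within the visit window, and dose only if the level is at least 20 ng/mL. Otherwise skip that dose and reassess at the next, on the model of 7.4.2. Leave the draw and recheck days to the sites within the existing windows (Day 180 +/-14, Day 270 +/-30), and note that this recheck is separate from the 8-week one in the charts.

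Vitamin D is already scheduled at both visits, so the text change is small. The costs are these.

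- Where the laboratory cannot report by the infusion visit, an earlier or extra draw is needed, possibly as a separate visit. Section 8.1.3 notes that Day 270 already falls outside standard follow-up.
- An unknown number of doses would be delayed or skipped. Skipping is more likely at Day 180, where the window is shorter.
- Skipped doses occur only in the pamidronate arm and would tend to dilute the intention-to-treat contrast (12.2). With 30 evaluable children in that arm (12.1), each affected child lowers the arm's simple mean by 1/30 of the benefit that child loses. The effect is slight if few are affected.

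If dosing through low vitamin D after dose 1 is intended, one sentence suffices instead: limit the contraindication statement in 6.2 to the first dose and say so.
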